### **3.3 Justification of the Study Design**

This is a study of safety, tolerability, PK, and PD of KM-819 administered orally to healthy adult and elderly subjects. A double-blind, placebo-controlled study is appropriate and standard for a SAD and MAD study. This design will minimize bias and provide reference data (i.e., data from placebo-treated subjects) which will aid in the interpretation of results.

Five SAD levels and four MAD levels are planned. The Principal Investigator (PI) and the Sponsor (both in a blinded state) will review available safety and PK data after each cohort to confirm whether it is safe to proceed with the next planned ascending dose, dose escalation should be stopped or the dose should be lowered or repeated in the subsequent cohort.

The safety assessments for the study are accepted measures for ensuring safety of patients during a clinical study. The times allowed for collection of PK/PD samples for KM-819 concentration are considered appropriate given the information available.

### **3.4 Dose Escalation Criteria**

In Part A, escalation to the next dose level will take place only after the safety and tolerability data for all subjects in the cohort (through Day 4) and available plasma PK data (through the 72-hour sample postdose) from the previously administered dose cohort has been reviewed. Data from exploratory PD assessments and CNS scales will not be included in the review for dose escalation decisions. Within the planned dose range a dose lower than the next planned dose level may be tested, depending on the emerging safety, tolerability, and/or other relevant data (e.g., plasma PK data).

### **3.5 Stopping Criteria for Dose Escalation**

Dosing will be stopped if 1 (or more) of the following apply. Depending on the nature of the AEs, it could be decided to investigate a lower dose level (intermediate between the current and the prior one) in the next group.

1. If 1 or more subjects experiences a study drug-related serious adverse event (SAE), unblinding of the subject(s) will be done. If the subject(s) was (were) on active treatment, dosing will be stopped.
2. If 2 subjects in 1 dose group show the following findings in 2 consecutive postdose measurements within 24 hours and if unblinding reveals that both subjects received active treatment, dosing will be stopped:
  - a. ALT or AST  $\geq 3 \times$  upper limit of normal (ULN) or,
  - b. ALT or AST  $\geq 2 \times$  ULN and ALT or AST  $\geq 5 \times$  baseline value or,
  - c. TBIL  $\geq 2 \times$  ULN
3. If 2 or more subjects in 1 cohort experience AEs of severe intensity or 4 or more subjects in 1 cohort experience AEs of moderate intensity, which are considered by the PI and/or Sponsor to be possibly or probably related to the investigational product, and of clinical concern, and if unblinding reveals that these subjects received active treatment, dosing will be stopped.

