### ***3.5.1 PK stopping criteria***

Due to the liver damage (higher ALT, ALP, GGT, and enlargement in common bile duct in liver) reported in one male dog following multiple dosing at 2000 mg/kg for 7 days, and NOAEL in male and female beagle dog at 1000 mg/kg/day for 14 days, the decision to escalate to the next planned dose will be based on review of PK exposure data from previous dose cohort(s). This will involve use of best available modeling practices of the observed AUC (i.e.,  $AUC_{\text{tau}}$  or  $AUC_{0-\infty}$ ) and  $C_{\text{max}}$  from each dose, resulting in a predictive distribution of AUC and  $C_{\text{max}}$  at higher dose levels. If predicted mean AUC and  $C_{\text{max}}$  for the next dose level is higher than 41.3 ug.h/mL and 9.3 ug/mL, respectively, then the dose escalation will stop and the Sponsor and PI will need to review the totality of data, including safety and PK before make any dose escalation decision. This PK stopping criteria are based on dog 2-Week study NOAEL exposure at 1000 mg/kg/day (the most conservative species and gender).

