#### 4.3 Subject Withdrawal and Replacement

A subject may withdraw from the study at any time without penalty and for any reason without prejudice to his/her future medical care. Participation of subjects may also be discontinued based on the medical judgment of the PI in conjunction with the Sponsor for any of the following reasons:

- ECG abnormalities:  
Any increases in QTcF > 500 msec or increase > 60 msec from baseline as confirmed with 3 consecutive ECGs taken within 5 minutes, with at least a 1-minute interval.
- Suicidality:  
Any suicide attempt or any recent suicidal ideation (a level of 4 or 5) since the last assessment, or a significant risk to commit suicide, as judged by the PI using the C-SSRS.
- Liver Safety Monitoring:  
Please refer to Stopping Criteria No. [2](#).
- After enrolment, the subject is found to violate the inclusion and/or exclusion criteria
- AE(s)
- Subject lost to follow-up
- Major protocol violation
- Use of prohibited medications mentioned in Section [5.8](#)
- The Investigator may, after discussion with the subject, withdraw the subject due to any serious safety concerns
- The study is terminated prematurely
- Other

In all cases, the reason(s) for withdrawal, and the primary reason, must be recorded on the electronic case report form (eCRF). Subjects who are withdrawn will have an Early Discontinuation (ED) Visit per the Schedules of Assessments (see Table [7-1](#) and Table [7-2](#)).

A subject may also be withdrawn from study by the Sponsor, Regulatory Authorities, or IECs/IRBs.

Subjects will also be withdrawn if the entire study is terminated prematurely as described in Section [9.10](#).

Withdrawn subjects may be replaced at the discretion of the Sponsor with agreement of the Investigator. Subjects who are discontinued because of treatment-emergent AE (TEAE) or possible toxic effects of the drug will not be replaced.

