#### 6.4.1.3.4 Adverse Events of Interest

An adverse event of interest (AEI) is an event which, in the evaluation of safety, has a special focus. An AEI is an AE (SAE or non-serious AE) which fulfils below defined AEI criteria:

- Potential Hy's law cases

Potential Hy's law, defined as  $\geq 3 \times$  ULN ALT with co-existing  $\geq 2 \times$  ULN bilirubin in the absence of  $\geq 2 \times$  ULN ALP, with no alternative explanation for the biochemical abnormality, must always be reported as an AE of interest (i.e., without waiting for any additional etiologic investigations to have been concluded). Follow-up information should then be reported if an alternative etiology is identified during investigation and monitoring of the subject.

AEI should be reported to the Sponsor/PAREXEL immediately (within 24 hours of the site being aware of the event).

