**PAREXEL International**  
**Toll free SAE [contact]-hour service)**  
**SAE [contact]**  
**Email: [Medical\\[contact]](mailto:[contact])**

#### *6.4.1.6 Follow-up of Adverse Events*

All AEs experienced by a subject, irrespective of the suspected causality, will be monitored until the AE has resolved, any abnormal laboratory values have returned to baseline or stabilized at a level acceptable to the PI, until there is a satisfactory explanation for the changes observed, until the subject is lost to follow-up, or until the subject has died.

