#### **6.4.2 Laboratory Variables**

Laboratory assessments will be performed locally at study center's laboratory by means of their established and validated methods. Before starting the study, the Investigator will supply PAREXEL/Kainos with a list of the normal ranges and units of measurement.

The Investigator may decide to repeat the tests, should the results be outside normal ranges and considered clinically relevant, or if the original sample could not be analyzed.

The following laboratory variables will be determined in accordance with the Schedule of Procedures (Table 7-1 and Table 7-2):

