**Table 6-2: Laboratory Assessments**

Test Group	Analyte/Component	Test Group	Analyte/Component
Hematology:	erythrocytes mean corpuscular volume (MCV) mean corpuscular hemoglobin (MCH) neutrophils eosinophils basophils lymphocytes monocytes platelets leukocytes hemoglobin hematocrit	Urinalysis:	pH protein glucose ketone bilirubin blood nitrite
Clinical chemistry:	albumin creatinine glucose urea uric acid total bilirubin (TBIL) direct bilirubin total protein triglycerides (TG) total cholesterol low-density lipoprotein (LDL) cholesterol high-density lipoprotein (HDL) cholesterol	Liver enzymes:	alkaline phosphatase (ALP) aspartate aminotransferase (AST) alanine aminotransferase (ALT) gamma-glutamyl transpeptidase (GGT)
Electrolytes:	sodium potassium calcium chloride	Serological marker:	Hepatitis B surface antigen (HbsAg) Anti-Hepatitis A Virus Immunoglobulin M (HAV IgM) Anti-Hepatitis C Virus (HCV Ab) Anti-Human immunodeficiency virus (HIV Ab)

Test Group	Analyte/Component	Test Group	Analyte/Component
Urine drug and cotinine screening, alcohol breath test	Amphetamines Barbiturates Benzodiazepines Cannabinoids Cocaine Opiates Cotinine Alcohol		

Clinical significance of out-of-range laboratory findings is to be determined and documented by the Investigator/sub-Investigator who is a qualified physician. Clinically relevant changes will be recorded as AEs in the eCRF (see Section 6.4.1.2).

For safety laboratory tests, the total volume of blood drawn will be approximately 51 mL for subject in Part A SAD and approximately 51 mL for subject in Part B MAD. Additional safety samples may be collected if clinically indicated at the discretion of the Investigator.

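### Liver stopping criterion 2 cannot be met on scheduled blood draws: it needs two values within 24 hours, draws are at least 48 hours apart, and no repeat has a deadline

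*Protocol*

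**What the plan says.** Criterion 2 in Protocol Section 3.5, repeated in the synopsis, opens: "If 2 subjects in 1 dose group show the following findings in 2 consecutive postdose measurements within 24 hours". The findings are (a) ALT or AST at least 3 x ULN, (b) ALT or AST at least 2 x ULN and at least 5 x baseline, or (c) total bilirubin at least 2 x ULN. If both subjects prove to have been on active drug, dosing stops.

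Sections 7.2.2 and 7.2.3 place post-dose biochemistry on Days 2, 7 and 14 in Part A and on Days 2, 4, 8 and 14 in Part B.

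On repeats, Section 6.4.2 says "The Investigator may decide to repeat the tests, should the results be outside normal ranges and considered clinically relevant", and the text after Table 6-2 adds "Additional safety samples may be collected if clinically indicated at the discretion of the Investigator". Section 6.4.1.6 requires adverse events to be monitored until, among other end points, "any abnormal laboratory values have returned to baseline or stabilized at a level acceptable to the PI". None of these gives a time limit.

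For an individual subject, the liver entry in Section 4.3 and the synopsis contains only a cross-reference to criterion 2.

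**The concern.** The rule asks for a confirmation interval that the schedule never provides. A mandatory stop therefore depends on an unscheduled sample whose timing is left open. Two active subjects with ALT at least 3 x ULN on Day 2 and no repeat within a day do not meet the criterion. They still do not meet it if both are again above the limit at the next scheduled draw.

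Liver injury is also the toxicity that the protocol cites when it sets its exposure limits: "Due to the liver damage (higher ALT, ALP, GGT, and enlargement in common bile duct in liver) reported in one male dog" (Section 3.5.1). In Part B, subjects would go on receiving daily doses while the stated liver rule stayed silent.

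**Working it through.** **Inputs.** Post-dose chemistry days are from Sections 7.2.2 and 7.2.3, the Day 14 window (±1 day) from Tables 7-1 and 7-2, PK sampling windows from Tables 7-3 and 7-4, the dosing window (8:00 to 10:00) from Section 7.2.3.1, and the Part A review cut-off (Day 4) from Section 3.4. The plan gives no figure of its own to reproduce here.

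**Step 1: gaps between scheduled draws.** Gap = difference in days x 24 h.

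| Part | Days | Gaps (h) | Within 24 h |
|---|---|---|---|
| A | 2, 7, 14 | 5 x 24 = 120; 7 x 24 = 168 | 0 of 2 |
| B | 2, 4, 8, 14 | 2 x 24 = 48; 4 x 24 = 96; 6 x 24 = 144 | 0 of 3 |

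The Day 14 window changes the last gap to 144–192 h in Part A and 120–168 h in Part B. If the last in-house Part B draw were on Day 7 instead of Day 8, the gaps would be 48, 72 and 168 h. The minimum stays at 120 h in Part A and 48 h in Part B. Reading the 24 hours as time since dosing does not help, because the schedule has no two post-dose chemistry draws in that period either.

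**Step 2: the Part B case.** Suppose two active subjects qualify on Day 2 and again on Day 4. Each has two consecutive qualifying measurements, but 48 h apart. Since 48 > 24, criterion 2 is not met.

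**Step 3: would a next-morning repeat fit?** The documents give only an 8 h fast for chemistry and no clock time. Assume that it is drawn with the morning PK sample.
- Part A, Day 2 to Day 3: the 24 h sample falls at 23.75–24.25 h and the 48 h sample at 47–49 h. The interval runs from 47 − 24.25 = 22.75 h to 49 − 23.75 = 25.25 h.
- Part B, predose to predose at a constant dosing time: 24 ± 0.5 = 23.5–24.5 h. With dosing anywhere from 8:00 to 10:00: 24 ± 2.5 = 21.5–26.5 h.

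A sensible next-morning repeat can thus fall outside 24 h and fail to count.

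**Step 4: what is exposed.** In Part A only 1 of 3 post-dose draws (Day 2) falls by the Day 4 cut-off, so scheduled data cannot meet criterion 2 before the escalation decision. No later dose remains for those subjects. In Part B, after the Day 2 dose, Days 3–7 leave 5 of 7 doses; after the Day 4 dose, Days 5–7 leave 3 of 7.

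**The case against.** The wording reads naturally as a confirmatory-repeat condition, and Section 6.4.2 allows the repeat. Subjects enter with liver enzymes and bilirubin not above ULN, so an investigator who sees ALT at 3 x ULN would very likely judge it clinically relevant. It then becomes an adverse event that must be followed. A reader might infer that nothing in the protocol requires re-measurement. That goes too far: for a change judged clinically relevant, follow-up is required and only its timing is open. The timing, however, is exactly what criterion 2 depends on.

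A reader might also infer that liver signals would pass unchecked and escalation would continue. The documents do not support that:
- Criterion 1 stops dosing on one drug-related SAE in an active subject.
- Criterion 3 stops it on 2 severe or 4 moderate related events of clinical concern in active subjects.
- The PK rule in Section 3.5.1 halts escalation, pending review, on predicted exposure.
- Potential Hy's law cases are reported within 24 h.
- The blinded PI and Sponsor "will review available safety and PK data after each cohort to confirm whether it is safe to proceed with the next planned ascending dose".

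These stand as safeguards but do not replace criterion 2. Criteria 1 and 3 depend on seriousness or intensity grading, and Section 6.4.1.3.2 grades intensity by tolerability and interference, so a symptomless enzyme rise may be called mild. The PK rule does not respond to observed enzymes. The Hy's law provision is a report, and it needs ALT and bilirubin raised together without ALP at 2 x ULN or more.

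On individual withdrawal, the cross-reference can fairly be read as importing only thresholds a to c. SAP Section 6.3.8 lists liver safety monitoring as a subject's own reason for discontinuation, with no two-subject condition. Section 4.3 also says "Participation of subjects may also be discontinued based on the medical judgment of the PI in conjunction with the Sponsor". It would be wrong to conclude that one subject cannot be withdrawn. What stands is that the text is ambiguous about the threshold.

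**Conclusion.** The point holds in a limited form. Criterion 2 cannot be met on scheduled data: 0 of 5 gaps between post-dose draws are within 24 h, and the smallest is 48 h. No text sets a deadline for the repeat that would satisfy it, and a persistent abnormality across two scheduled draws does not count. This is a defect of wording and timing in a stated safety rule, and it should be fixed. The rule is not inoperable, because a prompt discretionary repeat can meet it, and an early-discontinuation draw might do so by chance. The practical weight lies in Part B.

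The conclusion rests on nominal study days; the next-morning intervals rest additionally on the assumed draw time. No miss rate is offered, because the documents say neither how often qualifying values are expected nor how promptly investigators would repeat them.

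Criterion 3 names possible and probable relatedness but not definite, although Table 6-1 counts definite as related. A reader might infer that definitely related events are excluded. A minimum of possible is almost certainly meant, so this is an optional wording tidy-up and not part of the finding.

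**What to change.** **1. Criterion 2, in Section 3.5 and the synopsis.**
- Require a repeat ALT, AST and total bilirubin for any post-dose value meeting a, b or c. Take it as soon as possible and within 24 h of the site receiving the result; in Part B, before the next dose where feasible.
- Replace the two-measurements-in-24-hours condition with confirmation on the next post-dose measurement, whether repeat or scheduled. A late repeat, or the next scheduled draw, then still counts. Adding an hour or two to the present window would not be enough: it would still run from the sample rather than the result, and it could be missed after the outpatient draws.
- Require any pending repeat result before the escalation decision.

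**2. Individual liver ground, in Section 4.3 and the synopsis.** State that it is one subject with a confirmed value meeting a, b or c, without the two-subject and unblinding conditions.

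**Cost.** Amendment wording and an occasional extra blood sample. If results come back while subjects are in house or before an already planned visit, no extra visit is needed after 3 of the 7 post-dose draws (Part A Day 2; Part B Days 2 and 4). After Part B Day 8 the repeat means a longer stay or an extra visit, and after Part A Days 7 and 14 and Part B Day 14 an extra visit. The rule becomes slightly more sensitive.

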**Stopping Criteria for Dose Escalation:**

Dosing will be stopped if 1 (or more) of the following apply. Depending on the nature of the adverse events (AE)s, it could be decided to investigate a lower dose level (intermediate between the current and the prior one) in the next group.

1. If 1 or more subjects experiences a study drug-related serious adverse event (SAE), unblinding of the subject(s) will be done. If the subject(s) was (were) on active treatment, dosing will be stopped.
2. If 2 subjects in 1 dose group show the following findings in 2 consecutive postdose measurements within 24 hours and if unblinding reveals that both subjects received active treatment, dosing will be stopped:
  - a. ALT or AST  $\geq$  3 x ULN or,
  - b. ALT or AST  $\geq$  2 x ULN and ALT or AST  $\geq$  5 x baseline value or,
  - c. TBIL  $\geq$  2 x ULN
3. If 2 or more subjects in 1 cohort experience AEs of severe intensity or 4 or more subjects in 1 cohort experience AEs of moderate intensity, which are considered by the Principal Investigator (PI) and/or Sponsor to be possibly or probably related to the investigational product, and of clinical concern, and if unblinding reveals that these subjects received active treatment, dosing will be stopped.

stopped.

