### **5.5 Blinding and Breaking the Blind**

The study will be performed in a double-blind manner. All study drugs will be supplied in identical tablets and will be similar in color, smell, taste, and appearance, thereby enabling double-blind conditions.

For this study, the bioanalyst will be unblinded for dose escalation PK analysis.

For each randomized subject, an individual emergency (randomization) code break envelope will be stored in a secure location with access by designated staff members to open in the event of a medical emergency requiring knowledge of a subject’s treatment assignment.

The blind must only be broken following discussion on a case-by-case basis, at the discretion of the Sponsor/PI.

If the blind is broken, the date, time, and reason must be recorded in the subject’s eCRF, and any associated AE report.

If an emergency unblinding becomes necessary, the Investigator should notify the Sponsor/PI, if possible, prior to unblinding. The Investigator is responsible for opening the specified envelope, in the presence of a witness, both of whom must sign and date the envelope.

All envelopes, whether sealed or opened, must be returned to PAREXEL at the end of the study.

Serious unexpected suspected adverse reactions (SUSARs), which are subject to expedited reporting, should be unblinded before submission to the Regulatory Authorities.

The overall randomization code will be broken only for reporting purposes. This will occur once all final clinical data have been entered into the database and all data queries have been resolved, and the assignment of subjects to the analysis sets has been completed.

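### The safety stops wait for the treatment code to be read, but nothing requires dosing in the current cohort to be held until it is

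*Protocol*

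**What the plan says.** The synopsis and protocol Section 3.5 open the stopping rules in the same way: "Dosing will be stopped if 1 (or more) of the following apply". Each of the three criteria then makes the stop depend on the code.

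- **Criterion 1** (a drug-related SAE in one or more subjects): "unblinding of the subject(s) will be done. If the subject(s) was (were) on active treatment, dosing will be stopped".
- **Criterion 2** (ALT, AST or bilirubin findings in two subjects of a dose group): the findings must be present "in 2 consecutive postdose measurements within 24 hours", and then "if unblinding reveals that both subjects received active treatment, dosing will be stopped".
- **Criterion 3** (two or more subjects with severe AEs, or four or more with moderate AEs, judged related and of concern): "if unblinding reveals that these subjects received active treatment, dosing will be stopped".

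Section 5.5 gives the general rule on unblinding: "The blind must only be broken following discussion on a case-by-case basis, at the discretion of the Sponsor/PI". It describes sealed envelopes "with access by designated staff members to open in the event of a medical emergency", and for an emergency it says who acts: "The Investigator is responsible for opening the specified envelope, in the presence of a witness". It does not mention the stopping criteria.

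**The concern.** Making a stop depend on active treatment is a defensible choice. The gap is the interval between the clinical trigger, which is seen blinded, and the reading of the code. The protocol does not say that dosing pauses during that interval, and it does not say how long the interval may last.

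This matters most in Part B, where subjects are dosed daily for seven days. After a related SAE, paired liver findings or several severe AEs, whether the rest of the cohort receives the next dose rests on individual judgement. This is a first-in-human study in healthy volunteers, and Section 3.5.1 itself cites liver damage in one dog after 7 days of dosing at 2000 mg/kg. The liver rule has a further weakness: it depends on a second sample that the schedule does not provide.

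**Working it through.** The plan states no figure to reproduce. The check has three parts: what the text requires, when liver samples are taken, and how many doses could be affected.

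**1. Does any other section hold the cohort?**

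- Section 3.3 (blinded review after each cohort) and Section 3.4 (Part A review through Day 4) govern the move to the next dose level.
- Section 4.3 allows withdrawal of individual subjects at the PI's and Sponsor's judgement. Its liver entry points back to criterion 2.
- Section 9.10 allows termination of the whole study, after consultation.
- The Part A sentinel gap (Sections 3.1 and 4.5.2) is a minimum of 24 hours with no hold condition. It is specified for single-dose cohorts only.
- Section 5.5 asks for SUSARs to be unblinded before regulatory submission. Section 6.4.1.7 sets that at 7 or 15 calendar days after the Sponsor learns of the event. After the Day 1 dose, 7 − 1 = 6 dosing days remain, so neither limit secures unblinding before the course ends.

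None of these is a required hold.

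**2. Can criterion 2 be met on scheduled samples?** Postdose safety laboratory days come from Sections 7.2.2 and 7.2.3.

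- Part B: Days 2, 4 and 8, spaced about 48 and 96 hours apart, then follow-up on Day 14.
- Part A: Days 2, 7 and 14, spaced about 120 and 168 hours apart.

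Every gap exceeds 24 hours. The second value must therefore be an unscheduled repeat, which Section 6.4.2 leaves to the Investigator. After a raised Day 4 value in Part B, the next scheduled sample is Day 8, after the doses of Days 5, 6 and 7.

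**3. How many doses could be affected?** Inputs are 6 active subjects per cohort of 8 (Section 4.5.2) and once-daily dosing for 7 days in Part B (Section 3.1). Active doses per Part B cohort = 6 × 7 = 42. Let k be the number of triggering active subjects withdrawn.

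- Further active doses per day of delay = 6 − k.
- Upper bound after a Day 1 trigger, code unread until the course ends = 6 × (6 − k).

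| k | Per day of delay | Upper bound after Day 1 |
|---|---|---|
| 0 | 6 of 42 (14%) | 36 of 42 (86%) |
| 1 | 5 of 42 (12%) | 30 of 42 (71%) |
| 2 | 4 of 42 (10%) | 24 of 42 (57%) |

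With four withdrawn, as after four moderate AEs, each day allows 6 − 4 = 2 doses (5%). The Day 1 bound is for criteria 1 and 3. Criterion 2 would usually be met later, because the first scheduled postdose liver sample is on Day 2.

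In Part A each subject has one dose. After an event in the active sentinel, at most 6 − 1 = 5 of the 6 active doses are still to come. Only criterion 1 can be met at that stage, because just one of the two sentinels is on active drug and criteria 2 and 3 need at least two.

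**The case against.** The strongest reply is practical. Part B subjects are confined, each dose is supervised by the Investigator or qualified staff, AEs are assessed daily, and SAEs are reported within 24 hours. The person giving the dose knows of the event and can withhold it. Code envelopes already exist, and Section 6.4.2 allows repeat and additional laboratory samples. All of this stands, and it makes an informal pause likely. It still leaves the pause optional.

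Several stronger readings are tempting, and the documents do not support them.

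- *Section 5.5 forbids the unblinding that criterion 1 orders.* Criterion 1 is a specific mandatory rule beside a general one, and 5.5 itself provides for other unblinding (SUSARs, the bioanalyst). What is missing is a stated exception.
- *Criteria 2 and 3 leave the code unread.* Neither can be applied without reading it, so a code break is implied. It is simply not ordered or timed.
- *Criterion 2 can never be met.* It can, through a repeat sample. That repeat is optional.
- *A long run of extra doses is to be expected.* No document gives a delay, and the k = 0 row supposes that a subject with a related SAE goes on being dosed.

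One might also reply that 3.5 concerns escalation only, as its heading suggests. Its text says that dosing is stopped. If it meant escalation alone, the protocol would have no cohort-level rule for stopping daily dosing.

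**Conclusion.** The point holds and should be corrected. Followed as written, the protocol permits further doses to a cohort after a safety trigger while the code is unread, and it sets no effective time limit. It does not require those doses, and nothing shows that they would be given.

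The size depends on a delay that the documents do not state: up to 6 − k active doses per day in Part B, with 36, 30 or 24 of 42 as outer bounds after a Day 1 trigger. These are limits, not forecasts. They assume that all six active subjects are in the course, that the triggering subjects counted are on active drug, and that no informal pause is made. The exposure in Part A is smaller, at most five single doses. The finding on criterion 2 rests on the visit schedule alone and needs no assumption about delay.

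**What to change.** In Section 3.5 and the synopsis, keep every threshold, the active-treatment condition and the option of a lower dose level. Add:

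- (a) When the clinical condition in criterion 1, 2 or 3 is met on blinded data, dosing of all subjects in that cohort is suspended at once, including Part A subjects waiting behind the sentinel pair.
- (b) The triggering subjects are unblinded before the next scheduled dose.
- (c) If the active-treatment condition is not met, dosing resumes only on a documented decision of the PI and Sponsor.
- (d) A first liver value at a criterion 2 threshold is repeated within 24 hours, and that subject's next dose is withheld until the repeat is read. If two subjects have a first qualifying value, the whole cohort is held. Without (d), a daily dose could still fall between the two liver values.

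In Section 5.5, cross-refer to 3.5 as a mandatory exception to case-by-case discretion, limited to the triggering subjects and using the existing envelope procedure.

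**Cost.** Wording, one repeat liver sample per flagged subject, and loss of blind for the triggering subjects, so the Section 3.3 review is no longer fully blinded for them. If the code is not read before the 8:00–10:00 dosing window, a Part B dose is late or missed. That should be flagged in the steady-state analysis (SAP 6.3.12.5) and the accumulation ratios (SAP 6.1.3.1).

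Some holds will turn out unnecessary. Assuming events unrelated to treatment and 6:2 allocation, the active condition would fail in 1 − 6/8 = 25% of one-subject holds, 1 − 15/28 = 46% of two-subject holds and 1 − 15/70 = 79% of four-subject holds. For one sentinel subject, allocated 1:1, it is 50%. Each such hold costs a review and possibly one dose.
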